### **Minor Vascular Complications**

1. Access site or access-site related vascular injury (dissection, perforation, stenosis, hematoma, etc.) NOT leading to death, life-threatening or major bleeding, visceral ischemia, or neurological impairment
2. Distal embolization treated with embolectomy and/or thrombectomy and NOT resulting in amputation or end organ damage
3. Unplanned endovascular stenting or unplanned surgical intervention not meeting the criteria for a major vascular complication
4. Vascular repair or the need for vascular repair (via surgery, ultrasound-guided compression, transcatheter embolization, or stent-graft)
5. Percutaneous closure device failure
6. Failure of a closure device to achieve hemostasis at the arteriotomy site leading to alternative treatment (other than manual compression or adjunctive endovascular ballooning)

### **Table 6. Acute Kidney Injury (AKIN Classification)**

#### **Stage 1**

- Increase in serum creatinine to 150–199% (1.5–1.99 x increase compared with baseline) OR increase of >0.3 mg/dl (>26.4 mmol/l)

#### **Stage 2**

- Increase in serum creatinine to 200–299% (2.0–2.99 x increase compared with baseline)

#### **Stage 3**

- Increase in serum creatinine to >300% (>3 x increase compared with baseline) OR serum creatinine of >4.0 mg/dl (>354 mmol/l) with an acute increase of at least 0.5 mg/dl (44 mmol/l).

*The increase in creatinine must occur within 48 h. †Patients receiving renal replacement therapy are considered to meet Stage 3 criteria irrespective of other criteria.*

## **4.0 STUDY CONDUCT**

For the Schedule of Events refer to **Table 1**.

### **4.1 Screening**

Within 14 days prior to the procedure, the following baseline/screening assessments will be performed:

- Informed consent
- Assessment of eligibility
- Demographics
- Medical history
- Indication for endovascular procedure
- Physical exam
- Vital signs
- Hematology (refer to [Section 3.6.1](#))
- Blood chemistry (refer to [Section 3.6.1](#))

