**Table 1. Schedule of Events**

Procedure/ Assessment	Screening -14 to 0 days	Day of Procedure			
		Prior to large bore sheath Insertion	During procedure	Post-procedure	At discharge
Informed consent	X				
Eligibility	X				
Demographics	X				
Medical history/indication	X				
Concomitant medications	X				
Physical exam	X				
Serum CBC/Creatinine/PT- PTT/INR	X	X 		X 	X
Activated clotting time			X	X 	
Large bore endovascular access plan		X			
Contrast CT scan	X 				
Non-contrast CT scan	X 			X	
Saranas EBBMS insertion		X			
Saranas EBBMS monitoring			X 	X 	
Saranas EBBMS removal				X	
Adverse events		X	X	X	

1. Just after Saranas EBBMS insertion and before its activation
2. Immediately before Saranas EBBMS removal
3. If available per standard of care. May be performed up to 90 days prior to the procedure.
4. For up to 8 hours following procedure

[figure not shown]
**A CLINICAL STUDY TO EVALUATE THE SAFETY AND ACCURACY OF THE  
SARANAS EARLY BIRD™ BLEED MONITORING SYSTEM FOR THE DETECTION  
OF ENDOVASCULAR PROCEDURE RELATED BLEEDING EVENTS**

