### **4.3 Endovascular Procedure**

#### **4.3.1 Pre-Endovascular Procedures**

The following assessments and procedures will be performed prior to the endovascular procedure:

- The endovascular procedure will be planned.
- CT scans (with or without contrast) will be optimally (not mandatory) performed prior to the endovascular access procedure to assess for the presence of prior recent bleeding events or vascular complications (i.e. pseudonaeurysm, fistula). CT scan may be performed up to 90 days prior to the procedure.
- Assessment of baseline signs and symptoms

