#### **4.3.2 Endovascular Procedure**

The endovascular procedure will be performed in accordance with the institution's standard practices. The appropriate Saranas EBBMS sheath size will be selected, at the Investigator's discretion, and introduced per the Instructions for Use (refer to Appendix B). The data to be collected are as follows:

- Type of endovascular procedure

- Type of vessel cannulated with Saranas EBBMS (e.g. femoral artery, femoral vein)
- Access technique (e.g. ultrasound-guided, micro-puncture, anterior vs. posterior puncture)
- Large bore sheath size
- Type of large bore sheath
- Investigator's actions in response to any bleed detection, e.g. anti-thrombotic reversal, termination of the procedure, additional imaging or interventions.
- Recording of adverse events and/or device complications.

The Saranas EBBMS should be inserted in the femoral vein first. Blood sample (CBC, PT, PTT, INR, and creatinine) should be collected from the Saranas EBBMS after its insertion and prior to its activation. Afterwards, ipsilateral large bore access could be achieved.

During the endovascular procedure, the following assessments should be collected:

- Activated clotting time

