- Relationship between level (severity) of bleed detected by the Saranas EBBMS and the severity of bleeding as assessed by computerized tomography will be investigated. Summary statistics and interclass correlations will be calculated to assess the relationship between the two variables.
- Relationship between level (severity) of bleed detected by the Saranas EBBMS and the severity of bleeding as assessed by the absolute drop in hemoglobin from baseline will be investigated. Summary statistics and interclass correlations will be calculated to assess the relationship between the two variables.
- Relationship between level (severity) of bleed detected by the Saranas EBBMS and the number of transfusions will be investigated. Tabulations, summary statistics and interclass correlations will be used to describe the relationship between these two variables.
- Relationship between level (severity) of bleed detected by the Saranas EBBMS and the severity of bleeding as assessed by VARC-2 criteria will be investigated. Tabulations, summary statistics and interclass correlations will be used to describe the relationship between these two variables.
- Relationship between level (severity) of bleed detected by the Saranas EBBMS and the occurrence of post-procedural acute kidney injury will be investigated. Summary statistics and interclass correlations will be calculated to assess the relationship between the two variables.

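### No sample is named as baseline for hemoglobin and creatinine: the only laboratory set with that label is up to 14 days old, and the pre-activation sample has no analysis role

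*Combined protocol and SAP*

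**What the plan says.** Three analyses depend on a laboratory baseline.

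- Section 6.6.2 (Secondary Endpoints) relates EBBMS level to "severity of bleeding as assessed by the absolute drop in hemoglobin from baseline will be investigated".
- Table 6 (AKIN) stages kidney injury by the rise in creatinine relative to baseline, with the condition "The increase in creatinine must occur within 48 h". Section 6.6.2 limits the endpoint to post-procedural injury.
- Section 6.6.3 assesses laboratory safety by change from baseline.

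None of these sections identifies the sample. Elsewhere the protocol schedules two laboratory draws before monitoring starts:

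- **Screening.** Section 4.1 introduces its list with "Within 14 days prior to the procedure, the following baseline/screening assessments will be performed", and hematology and blood chemistry are on that list. Table 1 heads the same column "Screening -14 to 0 days", so this draw may also fall on the day of the procedure.
- **Pre-activation.** Table 1, footnote 1, places a draw "Just after Saranas EBBMS insertion and before its activation". Section 4.3.2 says that CBC, coagulation tests and creatinine "should be collected from the Saranas EBBMS after its insertion and prior to its activation", with large-bore access following. This draw is not called baseline anywhere.

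Section 4.3.1 also lists "Assessment of baseline signs and symptoms", but that is not a laboratory value. After the procedure, section 4.3.3 schedules one draw immediately before device removal and another before discharge. Section 6.6.2 does not say which of them ends the hemoglobin comparison.

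**The concern.** The device takes its own bioimpedance baseline after insertion (section 2.2). The IFU warns that it may miss bleeding that occurred before insertion or before the first bioimpedance measurement (IFU section 6). A hemoglobin change between screening and activation therefore cannot be reflected in EBBMS level. If the drop is computed from the screening value, that change is added to the severity measure as noise, or as a shift if hemoglobin tends to fall over the interval. The pre-activation sample avoids this, and because it precedes large-bore access it loses none of the bleeding from that puncture.

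The word baseline is attached to the less suitable of the two samples, so an analyst following the labels would probably choose it. Another analyst could choose the pre-activation value and equally claim to follow the plan. In an open-label study that choice should not be left until data are in hand.

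**Working it through.** **1. The plan's own figure.** The only design calculation is in section 6.1: 100 subjects, 5 with a bleed by either method, 2 discordant pairs, kappa 0.74, 95% CI 0.39 to 1.0. Kappa = (Po − Pe)/(1 − Pe).

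- Cells 3/1/1/95: Po = 0.98; Pe = 0.04² + 0.96² = 0.9232; kappa = 0.0568/0.0768 = 0.7396. With the large-sample standard error of 0.177, the lower limit is 0.7396 − 1.96 × 0.177 = 0.39, and the upper limit is truncated at 1.
- Cells 3/2/0/95: kappa = 0.7403, standard error 0.176, lower limit 0.40.

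The figure is reproduced. It uses no hemoglobin or creatinine value, so the choice of baseline does not change it.

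**2. Length of the gap.** At most 14 × 24 = 336 h from screening to procedure, and 336/48 = 7 times the AKIN limit. The minimum is same-day, because the window includes day 0.

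**3. Dilution of the hemoglobin relationship (illustration).** Let D be the drop during monitoring and P the change from screening to activation, with P independent of D and of EBBMS level L. The drop from screening is D + P, so

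corr(L, D + P) = corr(L, D) × SD(D)/√(SD(D)² + SD(P)²).

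The documents give neither standard deviation. Assumed ranges in g/dL:

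| SD(D) | SD(P) = 0.3 | SD(P) = 0.5 | SD(P) = 1.0 |
|---|---|---|---|
| 1.0 | 0.958 | 0.894 | 0.707 |
| 1.5 | 0.981 | 0.949 | 0.832 |

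**4. Effect on the computed drop (illustration).** Assume normal distributions and D with mean 1.5 and SD 1.0 g/dL. The share with a drop of at least 3 g/dL is:

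- from the pre-activation sample: P(Z ≥ (3 − 1.5)/1.0) = P(Z ≥ 1.5) = 6.7%;
- from screening, P with mean 0 and SD 0.5: P(Z ≥ 1.5/√1.25) = 9.0%;
- from screening, P with mean 0.5 and SD 0.5: P(Z ≥ 1.0/√1.25) = 18.6%.

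**5. Creatinine.** Take hypothetical values of 1.00 at screening, 1.35 before activation and 1.35 mg/dl after the procedure. The rise is 0.35 from screening, above the Stage 1 increment of 0.3, and 0 from the pre-activation sample. If the screening draw is more than 48 h older than the post-procedure draw, the comparison with screening cannot show that the rise fell within 48 h, so Table 6 does not allow it on that comparison alone. The two samples can give different answers, and the 48 h rule excludes the older one.

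**The case against.** The strongest reply is that the plan contains no rule to use the screening value. The baseline/screening label in section 4.1 is a lead-in that also covers consent, demographics and medical history; Table 1 calls the column screening only; and a dedicated pre-activation draw suggests use as the pre-monitoring reference. This stands as far as it goes. The defect is an undefined term, not a wrong rule, and a reader who infers that the screening value is the fixed analysis baseline goes beyond the text. It does not remove the problem, because the pre-activation draw is given no analysis role and the only label points the other way.

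Two further inferences are tempting and not supported.

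- *That the plan counts creatinine rises of up to 14 days as kidney injury.* The 48 h condition and the restriction to post-procedural injury block most of this. What remains is that the reference is unnamed and that an older screening value does not fit the rule.
- *That VARC-2 class is inflated.* Table 4 does not refer to a baseline, and its hemoglobin criteria also require overt bleeding. A fall before activation does not by itself make a major bleed. The direct effect is on the hemoglobin-drop endpoint.

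It is also fair to say that the pre-activation sample is not free of error. It is drawn through the device sheath, which the IFU has flushed with heparinized saline before insertion (12.1.5) and aspirated and flushed again before activation (12.2.6 to 12.2.8). The documents do not say whether the blood is drawn before or after the second flush. A diluted sample would lower the baseline hemoglobin and understate the drop. Stating the sampling order deals with this.

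**Conclusion.** The point holds as an undefined laboratory baseline, together with an unnamed end sample. If the screening value is used, hemoglobin change that the device cannot register enters the severity measure. The size cannot be found from the documents. Under the assumed standard deviations (1.0 to 1.5 g/dL during monitoring, 0.3 to 1.0 g/dL before it, independent of each other and of EBBMS level) the correlation with EBBMS level is multiplied by about 0.98 down to 0.71. Where screening is on the same day, the effect may be small. For kidney injury the conclusion is only that a screening creatinine more than 48 h older than the post-procedure value cannot serve as the AKIN reference.

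The endpoints affected are secondary and descriptive, plus the laboratory safety summary. The primary kappa, the comparison with CT and the sample size do not change. This is a cheap improvement worth making before analysis, not a threat to the main result.

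**What to change.** - In sections 6.6.2, 3.6.6 and 6.6.3, state that baseline hemoglobin and creatinine are the values from the sample drawn after EBBMS insertion and before activation.
- If that sample is missing, use the last earlier value, flag the subject, and repeat the analysis without flagged subjects. For kidney injury, use an earlier creatinine only if it fits the 48 h limit.
- Name the later sample that ends each comparison: before removal, before discharge, or the lowest hemoglobin and highest creatinine across both.
- In section 4.1, relabel the laboratory items as screening.
- State whether the pre-activation blood is drawn before or after the sheath is flushed, so that the baseline is not diluted.

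The cost is wording. The sample is already in the schedule, so no new visit or blood draw is needed. The remaining downside is the possible dilution and a flagged fallback value for any subject without the sample.

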### **4.2 Patient Enrollment**

After signing Informed Consent, and after study eligibility has been confirmed, patients will be enrolled in the study. A Subject Number will be assigned.

### **4.3 Endovascular Procedure**

#### **4.3.1 Pre-Endovascular Procedures**

The following assessments and procedures will be performed prior to the endovascular procedure:

- The endovascular procedure will be planned.
- CT scans (with or without contrast) will be optimally (not mandatory) performed prior to the endovascular access procedure to assess for the presence of prior recent bleeding events or vascular complications (i.e. pseudonaeurysm, fistula). CT scan may be performed up to 90 days prior to the procedure.
- Assessment of baseline signs and symptoms

#### **4.3.2 Endovascular Procedure**

The endovascular procedure will be performed in accordance with the institution's standard practices. The appropriate Saranas EBBMS sheath size will be selected, at the Investigator's discretion, and introduced per the Instructions for Use (refer to Appendix B). The data to be collected are as follows:

- Type of endovascular procedure

- Type of vessel cannulated with Saranas EBBMS (e.g. femoral artery, femoral vein)
- Access technique (e.g. ultrasound-guided, micro-puncture, anterior vs. posterior puncture)
- Large bore sheath size
- Type of large bore sheath
- Investigator's actions in response to any bleed detection, e.g. anti-thrombotic reversal, termination of the procedure, additional imaging or interventions.
- Recording of adverse events and/or device complications.

The Saranas EBBMS should be inserted in the femoral vein first. Blood sample (CBC, PT, PTT, INR, and creatinine) should be collected from the Saranas EBBMS after its insertion and prior to its activation. Afterwards, ipsilateral large bore access could be achieved.

During the endovascular procedure, the following assessments should be collected:

- Activated clotting time

#### 4.3.3 Post-Endovascular Procedure

After completion of the endovascular procedure the following assessments and procedures will be performed:

- Saranas EBBMS monitoring for up to 8 hours post-procedure
- A non-contrast CT scan (or contrast CT if clinically indicated or preferred) to identify or confirm any bleeds
- CBC, PT, PTT, INR, creatinine and activated clotting time should be collected immediately before removal of the Saranas EBBMS
- Removal of Saranas EBBMS
- Recording of adverse events and/or device complications
- Recording of the number of units of blood transfused
- Prior to discharge, serum CBC, PT, PTT, INR and creatinine
- Subject will be discharged
- Return of device to sponsor for assessment of impedance response.

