#### **3.6.2 Subject Monitoring and Care**

The institutions standard of care monitoring procedures and post-procedural care practices will be followed.

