## **6.0 STATISTICAL CONSIDERATIONS**

### **6.1 Patient Sample Size Requirements**

This study is intended to describe the accuracy and safety of the Saranas EBBMS. A sample of approximately 100 subjects should provide adequate evaluation of the planned endpoints. If 5%,  $n = 5$ , of subjects experience a bleed as detected by either the Saranas EBBMS or computerized tomography then the Kappa score remains above 0.7 when there are two or fewer discordant pairs. The 95% confidence interval with two discordant pairs and Kappa of 0.74 ranges from 0.39 to 1.0.

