### 6.6.4 General Statistical Issues

Descriptive statistics to be reported for each analyzed variable will include the number of observations, mean, median, standard deviation and range for quantitative variables, frequency and relative percent for ordinal and categorical variables.

Summary statistics will be displayed in tabular and/or graphical format. Missing data will not be interpolated, other than when a clinical assessment can replace a missing computerized tomography assessment. Any hypothesis tests will be performed using a two-sided significance level of 0.05. All computations will be performed using SAS®, version 9.1 or higher.

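### No post-procedure clinical bleeding assessment is fixed, so the composite secondary endpoints may be inflated where CT is negative or missing

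*Combined protocol and SAP*

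**What the plan says.** **Weight of clinical assessment.** Section 6.6.2 defines confirmed bleeds and false negatives against CT, clinical assessment or both. For composite agreement, sensitivity and specificity, a clinical bleed prevails over the CT result and over a missing CT. Section 6.6.4 allows clinical assessment as the only substitute for a missing CT. The primary endpoint and the CT-only sensitivity and specificity use CT alone, in the PP population.

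**What is scheduled.** Section 4.3.3 opens with "After completion of the endovascular procedure the following assessments and procedures will be performed". It then lists device monitoring, CT, laboratory tests before device removal and before discharge, adverse-event recording and units transfused. No access-site or bleeding examination appears. Table 1 marks "Physical exam" at screening only and has no vital-signs row.

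**What is named without a time.** Section 3.6.4 lists vital signs, and section 3.6.6 adopts VARC-2 for bleeding severity and vascular complications. Neither gives a post-procedure time point or an assessor. On routine care, section 3.6.2 says: "The institutions standard of care monitoring procedures and post-procedural care practices will be followed".

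**The alarm.** Section 3.5 describes an open-label study, and section 2.2 describes lights and audible alerts. Section 4.3.2 asks sites to record the investigator's "actions in response to any bleed detection, e.g. anti-thrombotic reversal, termination of the procedure, additional imaging or interventions".

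**The concern.** A reference standard should be applied in the same way whatever the index test shows. Here the CT part is planned for everyone, but the clinical part has no set time and no rule for what counts as a clinical bleed. It rests on local care at 5 to 10 sites and on adverse-event reporting, which section 5.1.1 bases on spontaneous reports and unprompted questions.

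The team sees and hears the alarm. If an alarm leads to a closer look, a bleed that CT does not show is more likely to be recorded with an alarm than without one. A bleed with neither an alarm nor a clinical record is then not counted as a false negative. Where CT was negative it is scored as a true negative. Where CT is missing, the plan does not say how an ITT subject with no recorded bleed is classified, but the false negative is lost either way.

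With the few bleeds expected, one such subject can visibly change composite sensitivity and kappa.

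**Working it through.** **1. The plan's own figure.** Section 6.1 states "A sample of approximately 100 subjects should provide adequate evaluation of the planned endpoints" and takes 5% (n = 5) "of subjects experience a bleed as detected by either the Saranas EBBMS or computerized tomography". It adds: "The 95% confidence interval with two discordant pairs and Kappa of 0.74 ranges from 0.39 to 1.0".

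Take N = 100, 3 subjects positive by both methods, 1 by the device only, 1 by CT only and 95 by neither:
- observed agreement = 98/100 = 0.98
- chance agreement = (4×4 + 96×96)/10,000 = 0.9232
- kappa = (0.98 − 0.9232)/(1 − 0.9232) = 0.74
- asymptotic SE = 0.177, so the 95% CI is 0.393 to 1.086, cut at 1.0

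The stated figure reproduces. It concerns the CT-only comparison, which this point leaves untouched.

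**2. Sensitivity of the composite to one unrecorded miss.** Assume the composite also has 5 bleeds: 3 detected, 2 missed, no false positives.

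| Missed bleeds unrecorded | Sensitivity | Kappa |
|---|---|---|
| 0 | 3/5 = 60% (exact 95% CI 15% to 95%) | (0.98 − 0.923)/0.077 = 0.74 |
| 1 | 3/4 = 75% | (0.99 − 0.9324)/0.0676 = 0.85 |
| 2 | 3/3 = 100% | 1.0 |

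These shifts can occur only for missed bleeds that CT does not show or where CT was not done. Specificity hardly moves: one extra true negative joins about 95.

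**3. Range of possible bias.** Let
- S = true sensitivity
- f = share of bleeds that only clinical assessment can reveal (CT negative or missing), the same with and without an alarm
- r = chance that such a bleed is recorded when there was no alarm, taken as 1 when there was an alarm

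Reported sensitivity = S / [S + (1 − S)(1 − f(1 − r))].

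The documents give none of S, f or r. With S = 62.5% assumed:

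| f | r = 0 | r = 0.5 |
|---|---|---|
| 0 | 62.5% | 62.5% |
| 10% | 0.625/(0.625 + 0.375×0.90) = 0.625/0.9625 = 65% | 0.625/(0.625 + 0.375×0.95) = 0.625/0.98125 = 64% |
| 25% | 0.625/(0.625 + 0.375×0.75) = 0.625/0.90625 = 69% | 0.625/(0.625 + 0.375×0.875) = 0.625/0.953125 = 66% |
| 50% | 0.625/(0.625 + 0.375×0.50) = 0.625/0.8125 = 77% | 0.625/(0.625 + 0.375×0.75) = 0.625/0.90625 = 69% |

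With r = 1 (equal ascertainment) every cell returns to 62.5%. With S = 70%, the range for r from 0.5 to 0 is 71% to 72% at f = 10% and 76% to 82% at f = 50%.

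**The case against.** The strongest reply is that the gap is one of timing and assessor, and that much is already collected from everyone. Section 3.6 says its listed assessments will be done, and these include vital signs and VARC-2 bleeding assessment. Whatever the alarm, section 4.3.3 plans CT, a blood count before device removal and before discharge, a transfusion count and adverse-event recording. Section 3.3.2 excludes patients who cannot have the CT, so missing scans should be uncommon. The device sits on the same side as the large-bore access, and its removal means each access groin is handled anyway. All of this stands, and it confines the risk to bleeds with negative or missing CT.

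It does not close the gap. Under VARC-2 a minor bleed, such as an access-site hematoma, has no hemoglobin or transfusion threshold, so someone has to look and record it. The synopsis makes CT conditional on medical feasibility and no section fixes its time, so a bleed after the scan enters the composite only through the clinical route.

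Two stronger inferences are tempting. A reader might conclude that subjects with an alarm are in fact examined harder and that missed bleeds are under-counted. The documents do not show this; section 4.3.2 only lists responses to be recorded. A reader might also build a large example: 8 bleeds, 5 with an alarm, and 2 of the 3 missed ones visible only on examination and never recorded, giving 5/6 = 83%. If 4 of the 8 bleeds are examination-only, that example assumes a 50% share and also weights it toward the missed bleeds. Nothing in the documents supports either assumption, and an equal 50% share gives 77%.

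The direction is not certain either. Action after an alarm could limit a bleed before CT and so lower agreement.

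**Conclusion.** The concern holds as a credible risk in a limited place. Clinical assessment can decide the composite reference, yet the plan sets no post-procedure time and no criteria for it, and the alarm is open to the people who make it. Composite agreement and sensitivity may therefore be inflated where CT is negative or missing. A reader might extend this to the primary endpoint, but that endpoint and the CT-only sensitivity and specificity do not use clinical assessment and are not affected by this mechanism.

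The size is unknown. From an assumed true sensitivity of 62.5%, and with no examination-only bleed recorded in the absence of an alarm, the reported value runs from about 65% (10% share) to 77% (50% share). It is smaller if some of those bleeds are recorded. At five bleeds the sampling uncertainty is wider than this bias. The bias still merits correction because it would not shrink with more subjects and is cheap to reduce.

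**What to change.** 1. **Table 1 and section 4.3.3:** add a standard access-site and vital-signs bleeding assessment, with bleed yes/no and VARC-2 class recorded in every subject whatever the alarm status. Do it immediately before EBBMS removal and at discharge, when blood is already drawn.
2. **Section 6.6.2:** define clinical assessment for the composite endpoints as these fixed assessments plus recorded adverse events.
3. **Section 6.6.2:** keep bleeds found only through alarm-triggered imaging out of the main composite analysis and report them in a sensitivity analysis.
4. **Limitations:** state that the examiner is not blinded to the alarm, so some dependence on it remains.

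The cost is one CRF page and a few minutes per subject. The new record would also supply the VARC-2 severity endpoint.
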